## **3.3 Key Secondary Efficacy Variables**

### **3.3.1 Change from baseline in loss of smell at Week 52**

Participant reported sense of smell will be evaluated as part of the NPSD. Loss of smell is captured by the DSS item (difficulty with sense of smell) in the NPSD asking participants to rate the severity of their worst difficulty with sense of smell over the past 24 hours using the following response options: 0 – None; 1 – Mild; 2 – Moderate; 3 – Severe. Baseline will be the mean of daily responses from Day -13 to Day 0. Bi-weekly (14-day) mean loss of smell will be calculated if at least 8 days in each 14-day period has evaluable data; otherwise the bi-weekly mean is set to missing.

### **3.3.2 Change from baseline in sinonasal outcome test score at Week 52**

The SNOT-22 is a condition-specific HRQoL assessment which captures participant-reported physical problems, functional limitations, and emotional consequences of sinonasal

conditions. Patient-reported symptom severity and symptom impact over the past 2 weeks are captured via a 6-point scale (0 = No Problem to 5 = Problem as bad as it can be). The total score is the sum of all item scores and has a range from 0 to 110 (higher scores indicate poorer outcomes). The total score and the changes from baseline will be calculated.

### **3.3.3 Time to (and proportion of participants with) nasal polyp surgery decision and/or systemic corticosteroids for nasal polyposis up to Week 52**

Surgery is defined as any procedure involving instruments resulting in incision and removal of tissue (e.g., polypectomy, endoscopic sinus surgery). Rescue treatment of NP is defined as requiring treatment with systemic corticosteroids (SCS) for at least 3 consecutive days (a single depo-injectable dose of corticosteroids will be considered equivalent to a 3-day course of systemic corticosteroids).

The following variables up to Week 52 will be derived for all participants:

- Time to first NP surgery decision or SCS for NP

*Time to first NP surgery decision or SCS for NP = (date of the first NP surgery decision or start date of first SCS for NP use – date of randomisation) + 1*

Participants who do not require NP surgery or do not receive SCS for NP will be censored on the date of the end of the planned treatment period defined in Section 3.1.3.

- Time to first NP surgery decision

*Time to first NP surgery decision = (date of the first NP surgery decision – date of randomisation) + 1*

Participants who do not require any NP surgery will be censored on the date of the end of the planned treatment period defined in Section 3.1.3.

- Time to first SCS use for NP

*Time to first SCS use for NP = (start date of the first SCS for NP use – date of randomisation) + 1*

Participants who do not receive SCS for NP will be censored on the date of the end of the planned treatment period defined in Section 3.1.3.

Kaplan-Meier methods will be used to estimate the cumulative proportion of participants who had NP surgery decision, SCS for NP, and NP surgery decision or SCS for NP up to Week 52.

Time to first NP surgery and time to first NP surgery or SCS for NP will be derived in a similar way but based on the actual surgery date.

### 3.3.4 Change from baseline in Lund Mackay score (LMK) at Week 52

The LMK score provides a semi-quantitative assessment of nasal sinuses on sinus CT scans and will be used to assess sinus opacification. Based on the sinus CT images, the five sinuses (maxillary, anterior ethmoid, posterior ethmoid, sphenoid and frontal) on each side are scored by central radiologist as follows:

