7.2 Lost to Follow-up

A participant will be considered lost to follow-up if he or she repeatedly fails to return for scheduled visits and is unable to be contacted by the study site.

The participant is considered lost to follow-up when any of the following attempts to contact fails: 3 attempts of either phone calls, faxes, or emails; having sent 1 registered/certified mail; and 1 unsuccessful effort to check the vital status of the participant using publicly available sources, if allowed, by local regulations.

The following actions must be taken if a participant fails to return to the clinic for a required study visit:

- The site must attempt to contact the participant and reschedule the missed visit as soon as possible and counsel the participant on the importance of maintaining the assigned visit schedule and ascertain whether or not the participant wishes to and/or should continue in the study.
- Before a participant is deemed lost to follow-up, the investigator or designee must make every effort to regain contact with the participant (where possible, 3 telephone calls and, if necessary, a certified letter to the participant's last known mailing address or local equivalent methods). These contact attempts should be documented in the participant's medical record.
- Efforts to reach the participant should continue until the end of the study. Should the participant be unreachable at the end of the study the participant should be considered lost to follow-up with unknown vital status at end of study and censored at latest follow-up contact.
- Site personnel, or an independent third party, will attempt to collect the vital status of the participant within legal and ethical boundaries for all participants randomised, including those who did not get investigational product. Public sources may be searched for vital status information. If vital status is determined as deceased, this will be documented, and the participant will not be considered lost to follow-up. Sponsor personnel will not be involved in any attempts to collect vital status information.

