9.2 Sample Size Determination

Approximately 400 participants will be randomised to tezepelumab 210 mg Q4W or matching placebo in a 1:1 ratio.

The study is sized to provide compelling statistical evidence for the co-primary endpoints (NPS and NCS) and key secondary endpoints of change from baseline in loss of smell, LMK, and SNOT-22 (considering a significance level of 0.01 in the sample size calculations), as well as sufficient power to assess the composite endpoint of time to SCS and/or surgery (2-sided level of 1%). In addition, this sample size allows assessment of the effect of tezepelumab vs placebo on NPS and NCS in key subgroups and provides a reasonably-sized safety database.

Assuming a population standard deviation (SD) of 2.25 in total NPS change from baseline and 1.22 in NCS change from baseline, this sample size of 200 participants per arm will provide at least 95% total power to observe a statistically significant difference at a 2-sided 1% level on both co-primary endpoints if the true effect of tezepelumab is -1.8 in total NPS change from baseline and -0.87 in NCS change from baseline. The assumption of true effects is based on reported estimates in the dupilumab Phase III nasal polyp studies. It is expected that treatment with tezepelumab will demonstrate similar or better treatment effects over a 52-week period. The assumed SD was estimated based on the CIs of the corresponding endpoints in the dupilumab Phase III nasal polyp studies ([Bachert et al 2019](#)).

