9.4.2.2 Secondary Endpoint(s)

The analyses of the key secondary endpoints are described as follows:

The change from baseline in LMK, SNOT-22, loss of smell, and NPSD TSS at Week 52 will be analysed using the method as described in the primary analyses approach for the co-primary endpoints.

Time to first decision of surgery or SCS for NP during the 52-week treatment period will be analysed using a Cox proportional hazards model, adjusting for treatment, baseline co-morbid asthma/AERD/NSAID-ERD status, prior surgery status, and regions. The event of interest is the first SCS use or decision for nasal polyp surgery, whichever is earlier if both occur. Hazard ratios and corresponding 95% CIs and p-values will be presented. The proportion of participants having a surgery decision or SCS up to Week 52 will be estimated using the Kaplan-Meier method. The same method will be used to analyse the time to first surgery decision and time to first SCS separately.

Analysis of the change from baseline in FEV1 at Week 52 will use a treatment policy for all intercurrent events defined in Section 9.4.1.1. The population of interest will be the subset of participants with baseline co-morbid asthma/AERD/NSAID-ERD. The model includes baseline value of FEV1 as a covariate and treatment, prior surgery status, and regions as factors.

Details on statistical analyses for other secondary endpoints, including the tezepelumab serum

concentration and ADA for the evaluation of PK and immunogenicity, will be provided in the SAP.

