### 3.1.3 Study Periods

The following study periods are defined for analysis purposes:

- **Screening/run-in period:** starting on the date of the first study procedure and ending one day prior to randomisation (for randomised participants) or on the date of the last study procedure (for screening failures). If any participant is re-screened, the latest available screening will be used for this purpose.
- **Planned treatment period:** starting on the date of randomisation (efficacy) and ending on the date of the Week 52 visit or earlier study withdrawal date (for participants not followed up until Week 52). Unless noted otherwise, efficacy analyses will be based on planned treatment period.
- **On-treatment period:** starting on the date of first dose of IP and ending on the earlier (date of last dose of IP + 33 days, date of study withdrawal). Note: The 33 days is derived as dose frequency (28 days) plus 5 days as specified in the CSP Section 1.3.

- **Post-treatment period:** starting on the day after the end of the on-treatment period until the end of the study (Week 76 for the first ~200 participants and Week 64 for the remaining participants) or early withdrawal date.
- **On-study period** (planned treatment and follow-up): starting on the date of randomisation (efficacy) / date of first dose of IP (safety) and ending on the study completion or withdrawal date. For analyses performed at primary database lock, the on-study period is understood to include all data recorded up until the date of the data cut-off for the primary database lock (which includes all follow-up data available at the time of the data cut-off).
- **Additional FU period:** starting on the day after Week 64 visit until the end of the study (Week 76) or early withdrawal date. Only the first ~ 200 participants will continue follow-up beyond Week 64.

If a participant dies, the end dates of the study periods defined above will be capped at the date of death.

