#### Time to premature study withdrawal

Time to premature study withdrawal will be defined as follows:

$$\text{Time to premature study withdrawal (days)} = [\text{study withdrawal date from eCRF} - \text{date of randomisation}] + 1.$$

Study withdrawal date will be the completion or discontinuation date from the “Disposition” eCRF page, where any participant status other than “Completed” has been entered.

Participants who did not prematurely withdraw from study will be censored at one of the following dates:

- Completion or discontinuation date from the “Disposition” eCRF page, where participant status of “Completed” has been entered.
- At primary database lock (DBL), ongoing participants will be censored at data cut-off date.

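### For participants lost to follow-up, the SAP's censoring date for H02d, H03 and H04 is not tied to last contact as in Protocol 7.2, and in some cases is undefined (minor)

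*SAP*

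**What the plan says.** **Protocol.** Section 7.2 says of a missing participant: "Efforts to reach the participant should continue until the end of the study". One who is still unreachable then is to be "considered lost to follow-up with unknown vital status at end of study and censored at latest follow-up contact". The sentence names no endpoint. Section 9.4.2.2 sets the analysis of the composite ("Time to first decision of surgery or SCS for NP during the 52-week treatment period will be analysed using a Cox proportional hazards model") and applies the same method to each component, but gives no censoring date.

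**SAP.** Section 3.3.3 covers all three time-to-event key secondary endpoints: the composite (H02d), surgery decision (H03) and SCS (H04). In each, participants without the event "will be censored on the date of the end of the planned treatment period defined in Section 3.1.3". Section 3.1.3 defines that period as "ending on the date of the Week 52 visit or earlier study withdrawal date (for participants not followed up until Week 52". The withdrawal date is defined only in 3.1.8, for the disposition plots: "Study withdrawal date will be the completion or discontinuation date from the" Disposition eCRF page. Nothing links it to the last contact.

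The SAP's opening section undertakes to describe any change from the protocol. Section 6 lists only added exploratory analyses.

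**The concern.** A date on a disposition form need not be the date a participant was last seen or spoken to. Under Protocol 7.2 the search continues to the end of the study, which Protocol 4.4 sets by the last participant globally. If a site enters the date on which loss was declared, the months since last contact enter the Cox and Kaplan-Meier analyses as time observed without an event. Nobody asked about corticosteroids or surgery decisions in those months, so they are not follow-up.

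There is also a gap in the definition. SAP 3.1.3 offers a Week 52 visit or an earlier withdrawal. A participant with no Week 52 visit whose withdrawal is recorded after Week 52 fits neither. Nor does one still being sought at the primary lock, which takes place once the last participant completes Week 52. A programmer would have to invent a rule.

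At stake are three endpoints under multiplicity control. The planned supportive analyses (SAP 4.2.7.2.3 and 4.2.7.2.4) change the event definition, not the censoring, so they would not show the problem.

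**Working it through.** **Inputs from the documents** (Protocol 9.2): participants "randomised to tezepelumab 210 mg Q4W or matching placebo in a 1:1 ratio", with "this sample size of 200 participants per arm"; HR 0.33; placebo Week 52 rate 35% (H02d) and 11% (H03); two-sided 1% for H02d and nominal 5% for H03, taken as two-sided. No effect size is stated for H04.

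**Inputs assumed.** The documents give neither a loss rate nor a gap between last contact and withdrawal date. I take 2-10% lost per arm; last contact uniform over the 52 weeks; a gap of 4 weeks, 12 weeks or up to Week 52; constant hazards; and loss unrelated to outcome.

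**Step 1: the plan's own figures.** Expected events are 200p + 200[1 − (1 − p)^0.33]. Schoenfeld power is Φ(√(d/4)·|ln 0.33| − z).

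- H02d: 70.0 + 26.5 = 96.5 events; √(96.5/4) × 1.109 − 2.576 = 2.87; power 99.8%. The stated figure of at least 95% reproduces.
- H03: 22.0 + 7.5 = 29.5 events; √(29.5/4) × 1.109 − 1.960 = 1.05; power 85.4%. The stated figure of at least 80% reproduces. Freedman's formula gives 78.2% and a comparison of proportions 79.1%.

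**Step 2: formulas for the censoring date.** Time is in years, hazard λ, fraction lost L.

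- Week 52 risk with full follow-up: a = 1 − e^(−λ).
- Probability that a lost participant has the event before last contact: b = 1 − a/λ.
- Events per participant: E = (1 − L)a + Lb.
- Time at risk to last contact: T = E/λ.
- Extra event-free time if the gap runs to Week 52: X = Lb/λ.

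Censoring at last contact gives the rate E/T = λ. The later date gives E/(T + X). The HR is the ratio of the two arms' rates, and the Week 52 risk is 1 − exp(−rate). For shorter gaps, X is L times the mean of e^(−λu)·min(gap, 1 − u).

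**Step 3: one case in full.** H02d, 10% lost on placebo, 2% on tezepelumab, gap to Week 52.

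- Placebo: λ = −ln 0.65 = 0.4308; a = 0.350; b = 0.1875; E = 0.3338; T = 0.7748; X = 0.0435; rate 0.3338/0.8183 = 0.4079. Risk falls from 35.0% to 33.5%.
- Tezepelumab: λ = 0.33 × 0.4308 = 0.1422; a = 0.1325; b = 0.0678; E = 0.1312; T = 0.9231; X = 0.0095; rate 0.1312/0.9326 = 0.1407.
- HR = 0.1407/0.4079 = 0.345, against 0.330 with censoring at last contact.

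**Step 4: the range for H02d.**

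| Lost, placebo / tezepelumab | HR, 4-week gap | HR, 12-week gap | HR, gap to Week 52 |
|---|---|---|---|
| 5% / 5% | 0.330 | 0.330 | 0.330 |
| 10% / 10% | 0.330 | 0.330 | 0.331 |
| 10% / 5% | 0.331 | 0.334 | 0.340 |
| 5% / 10% | 0.329 | 0.326 | 0.322 |
| 10% / 2% | 0.332 | 0.336 | 0.345 |
| 2% / 10% | 0.328 | 0.324 | 0.317 |

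H03 agrees to within 0.001 (0.317 to 0.344). With 10% lost on placebo and the gap to Week 52, its placebo risk falls from 11.0% to 10.5%.

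**Step 5: scale.**

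- The largest H02d shift is ln(0.345/0.330) = 0.044. The standard error of the log HR is about √(1/70 + 1/26.5) = 0.23, so the shift is about a fifth of one standard error.
- The placebo proportion moves by at most 1.5 points against a standard error of √(0.35 × 0.65/200) = 3.4 points.
- The number of observed events does not depend on the censoring date. At these losses, Schoenfeld power at HR 0.33 is about 99.7% for H02d and 83.6-84.7% for H03.

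**The case against.** The strongest reply is that there is no contradiction to resolve. Protocol 7.2 is a procedural section about participants of unknown vital status and names no endpoint. Section 9.4.2.2 sets no censoring date, and Section 9.4 leaves detailed data handling to the SAP. This stands in part: 7.2 cannot be cited as the prescribed rule for H02d, H03 and H04. But censoring has meaning only in a time-to-event analysis, these are the trial's only confirmatory ones, and the SAP neither adopts 7.2 nor declares a departure from it.

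The second reply is that few participants are affected. Under Protocol 7.1.1, someone leaving follow-up option 1 or 2 completes the end-of-treatment visit at once, option 3 participants are contacted at Week 52, and a withdrawal visit is expected when consent is withdrawn. That stands. It leaves those truly lost, whose number is unknown.

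Three stronger readings are tempting, and the documents do not support them:

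- *That lost participants are carried to a later visit.* SAP 3.1.3 takes the Week 52 visit or an earlier withdrawal date, and anyone who attended Week 52 was observed to that point.
- *That unobserved time is certain to be counted.* The Disposition date may already be entered as the last contact; the documents do not say how it is set for lost participants.
- *That the missing Week 52 cap distorts H02d to H04.* Events are counted only up to Week 52, so later time at risk changes neither the Cox estimate nor the Kaplan-Meier estimate at Week 52. It does matter for the time at risk in the SCS course rate (SAP 4.2.8.8), which is built from the same period.

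**Conclusion.** The point holds as a minor one. The two documents describe different stopping points for lost participants, the SAP's date is not tied to observation, and for some participants it is undefined.

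A reader might infer a bias in a known direction, or a threat to the confirmatory conclusions. Neither follows. With equal loss the HR does not move materially. With unequal loss it moves towards 1 if more are lost on placebo and away from 1 if more are lost on tezepelumab. Placebo Week 52 risk falls by at most about 1.5 points for the composite and 0.5 points for surgery decision.

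These sizes rest on the assumed losses and gaps, constant hazards and non-informative loss. Loss related to outcome was not examined. Nor was any effect on adverse event rates quantified, so none is claimed.

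**What to change.** In SAP 3.1.3 and 3.3.3, censor event-free participants at the earliest of:

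- Day 365;
- the Week 52 visit, or the Week 52 contact for participants on follow-up option 3;
- the last contact at which SCS use and surgery-decision status was ascertained.

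Use the same end date for the time at risk in 4.2.8.8. The ascertainment condition goes further than Protocol 7.2, which says only latest contact, so it should be presented as a clarification.

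If the sponsor prefers to keep the Disposition date, either define it as the last contact for participants lost to follow-up, or record the departure from Protocol 7.2 in Section 6. In either case, state the end date for someone with no Week 52 visit and no earlier withdrawal date.

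The cost is a few sentences and one derived date. If gaps exist, the reported event proportions rise slightly. The change belongs before the primary lock, because SAP 2.1.4 rules out later updates.

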**Table 5 Lund-Mackay score**

Score	CT scan assessment
0	No abnormality
1	Partial opacification
2	Total opacification

The osteomeatal complex (Table 6) is scored for the right and left sides as follows:

**Table 6 Osteomeatal complex score**

Score	CT scan assessment
0	Not occluded
2	Occluded

The maximum total LMK score is 24. The change from baseline in LMK score evaluated by CT at Week 52 will be presented as a key secondary endpoint.

### 3.3.5 Change from baseline in NPSD total symptom score at Week 52

The NPSD TSS consists of 8 out of the 11-items on the NPSD symptom diary, which evaluates a participant's experience with NP over the past 24 hours. The 8 items supporting the TSS ask participants to report their experience with nasal blockage, NC, runny nose, postnasal drip (mucus drainage down the throat), headache, facial pain, facial pressure, and difficulty with sense of smell. Participants report the severity of each symptom at its worst using a 4-point verbal rating scale (0-None to 3-Severe). The TSS is calculated by taking the sum of the 8 equally weighted symptom items. The total TSS and the changes from baseline will be calculated.

### **3.3.6 Change from baseline in pre-BD FEV1 at Week 52 (in participants with co-morbid asthma/AERD/NSAID-ERD)**

Lung function in participants with co-morbid asthma/AERD/NSAID-ERD will be measured by spirometry and assessed using FEV1. Only those spirometry tracings determined to be acceptable or borderline will be used. The measurement used in the analysis is the one marked with Best Result Flag (not necessarily the highest) equal to “Yes” as per Data Transfer Specification. The change from baseline in pre-BD FEV1 at Week 52 will be presented.

## **3.4 Other Secondary Efficacy Variables**

### **3.4.1 Change from baseline in nasal polyp score through Week 52**

The total NPS evaluated by nasal endoscopy over time through Week 52 (Baseline, Weeks 4, 12, 24, 36, 52) will be evaluated as described in Section 3.2.1 above. Additionally, the proportion of participants with a  $\geq 1$  point reduction and a  $\geq 2$  points reduction in NPS through Week 52 will be presented.

### **3.4.2 Change from baseline in nasal congestion score through Week 52**

Participant reported NC evaluated as part of the NPSD over time through Week 52 (every 14-days) will be evaluated as described in Section 3.2.2 above.

### **3.4.3 Change from baseline in UPSIT test at Week 52**

Participant reported loss of smell will be evaluated using the University of Pennsylvania Smell Identification Test (UPSIT) test of olfactory function which uses microencapsulated odorants that are released by scratching standardized odour-impregnated test booklets (Doty et al 1984). Four booklets with 10 odorants each are used for the test. Participants are asked to identify the odour using multiple choice format which lists different possibilities. Scores are based on number of correctly identified odours with a total score ranging from 0 to 40. The olfactory diagnosis will be classified based on the test scores by gender (male vs female) as listed in Table 7.

**Table 7 UPSIT Olfactory Diagnosis**

Olfactory Diagnosis	Test Scores (Male)	Test Scores (Female)
Anosmia	00 - 18	00 - 18
Severe Microsmia	19 - 25	19 – 25
Moderate Microsmia	26 - 29	26 – 30
Mild Microsmia	30 - 33	31 – 34
Normosmia	34 - 40	35 - 40

### 3.4.4 Change from baseline in modified LMK score at Week 52

The modified Lund-Mackay or Zinreich scoring system will be utilized to score the same CT images scored using the LMK to assess sinus opacification. Based on the sinus CT images, the five sinuses (maxillary, anterior ethmoid, posterior ethmoid, sphenoid and frontal) on each side will be scored based on the percentage of opacification from mucosal thickening according to [Table 8](#).

